- J. If the research requires the access, use, or disclosure of any of the 18 individually identifiable protected health information (PHI) identifiers that can be used to identify, contact, or locate a person (e.g., name, medical record number, etc.), are the subjects going to consent to or authorize the disclosure of their individually identifiable health information? *The research requires the access, use, or disclosure of one or more of the 18 individually identifiable protected health information (PHI) identifiers, as noted in 47I and the subjects will consent to or authorize the disclosure of their individually identifiable health information.*
 - a. *Or* is HIPAA authorization altered or waived? *No. HIPAA authorization is not altered or waived.*
- K. What is the classification of the data (de-identified, limited data set, protected health information, other). *protected health and identifiable information*
- L. Does the request to transfer/share data include clinical data that belongs to the UNM Health Systems? *Yes*
- M. Does the data to be transferred/shared include information about patients seen at external health system or at a third party medical provider? *No*
- N. Is the external entity a “covered entity”? *Yes*
- O. Is the data that is going to be transferred/shared owned or partially owned by another party or have any type of restrictions including regulatory restrictions (i.e. HIPAA, FERPA, etc.)? *No*

PROTOCOL TITLE: Keeping rural minority ‘essential’ workplaces open safely during the COVID-19 pandemic: The role of frequent point-of-care molecular workplace surveillance for miners

P. Is the data publically available? If yes, please provide details: *No*

Q. Does the data include information about substance abuse treatment, sexually transmitted diseases, genetic testing results, HIV/AIDS testing results, and/or mental health? *No*

48.Specimen Transfer/Sharing (Checklist) (required –do not delete even if the answer is “No”)

Provide all requested information if the research involves transferring/sharing of specimens with an external entity (institution, company, etc.).

A. Will specimens be transferred/shared with an external entity (institution, company, etc.)?

Yes

No. **The remainder of this section does not apply.**

B. Indicate if the specimens are incoming and/or outgoing: *NA*

C. Provide the name of the entity that specimens will be being transferred/shared with: *NA*

D. Provide the contact name, email and phone number with whom specimens are being transferred/shared with: *NA*

E. Who is responsible for sending out the specimens? Please note specimens cannot be sent out without a fully executed material transfer agreement.

NA

F. Who is responsible for receipt of the specimens? Please note specimens cannot be received without a fully executed material transfer agreement.

NA

G. For specimens being transferred/shared with outside locations or entities, describe the following:

Where is specimen storage and how will it be maintained in a secure manner? *NA*

- What is method in which specimens will be collected and stored? *NA*
- How long will the specimens be stored? *NA*

Who will have access to the specimens? *NA*

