In a 2016 study at the intervention mine, we determined that 58% of miners used social media, 91% reported Internet access over their telephone, and 92% used the phone for texting. Miners reported using social media for 51 (mean) \pm 142 (SD) minutes daily for 6 \pm 5 years, indicating adept and frequent usage. 52% of those surveyed indicated an interest in using social media to receive information about miners’ projects from our group. The social media-savvy nature of rural NM miners, initially surprising to our group, is a novel way to reach out to the study population using phone/web apps, which will be developed by Ingenuity Software Labs, Albuquerque, New Mexico. Our mine safety officer partner, [name], CMSp, helped establish our social media engagement and education plan, including a video tutorial.

[figure not shown]
Table 4: List of study SARS-CoV-2 tests

SARS-CoV-2 test	FDA authorized
Screening test (molecular)	Yes
Diagnostic test (RT-PCR)	Yes
Serologic antibody test	Yes
Viral burden (Quantitative RT-PCR or RT-qPCR)	Research test

Our capacity for SARS-CoV-2 testing: Molecular tests help establish a diagnosis by detecting SARS-CoV-2 nucleic acids using RT-PCR or nucleic acid amplification assays (23). Laboratory-based RT-PCR assays performed on nasopharyngeal (NP) swabs collected by trained professionals (i.e., diagnostic test) are the cornerstone of diagnostic testing. A recent study showed that unsupervised, self-collected, midnasal swabs for the

detection of SARS-CoV-2 are comparable to clinician-collected nasopharyngeal swabs (Cohen K statistic = 0.81), offering a unique opportunity to scale-up workplace testing (24). The commercial choice of screening test for our study will be finalized, based on test availability, in collaboration with the NIH RADx-UP initiative, but will have the following characteristics (Regulatory status: All; Diagnostic target: Viral antigen; Analysis location: Self or Lab CLIA Waived; Platform: Lateral flow; Specimen collected: Nasal swab; Company: Any; Minutes to result: 30 minutes or less; Sensitivity and specificity: At least 80%)..

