Effective molecular surveillance may be only marginally affected by a test’s lower analytical limits of detection (26). Although molecular tests may show false negatives (FN) early on or late in the infection cycle when viral load is increasing and decreasing, respectively, the viral burden corresponding to a positive screening test is not established (29). Interim results demonstrate that when compared to the diagnostic (laboratory-based qualitative RT-PCR), screening test in controlled settings (in urgent care clinic, hospitalized and nursing home patients) is $\geq 95\%$ sensitive and $\geq 99\%$ specific (30). In our study, the screening test utilizes samples collected: a) at the workplace, b) by the participant, c) using nasal swabs followed by point-of-care testing, d) in a low infrastructure community setting, e) by minimally trained professionals. The screening test was granted emergency use authorization without a detailed study on end-user needs in the real-world, but each of the above variables introduces a potential source of error in results.

PROTOCOL TITLE: Keeping rural minority ‘essential’ workplaces open safely during the COVID-19 pandemic: The role of frequent point-of-care molecular workplace surveillance for miners

Our *objective* is to determine the ability of the screening test to correctly detect the presence of the virus in upper respiratory specimens in the real-world setting. This will be accomplished by evaluating screening test performance at the workplace by quantifying viral loads from self-collected nasal swab and health personnel-collected nasopharyngeal (NP) swab specimens, using quantitative RT-PCR (RT-qPCR). Our *working hypothesis* is that the sensitivity of the screening test in a real-world study setting is a) comparable to that described by others in controlled settings, and b) positively associated with viral load in upper respiratory specimens. Successful completion of this study will help determine the real-world performance of less sensitive screening tests in disease settings of mild severity.

Table 5: Test findings studied in Aim 2

Measurement	Biological specimen	N	Purpose
Screening test (qualitative)	Self-collected nasal swab	less than 250	Workplace surveillance
Diagnostic test RT-PCR (qualitative)	Healthcare personnel collected NP swab	less than 250	Establish sensitivity, specificity & diagnostic accuracy of screening test

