Power calculations: If we recruit less than 250 miners, we have the power to estimate 85% acceptance rate \pm 4.6%. For a comparison of acceptance rates between predictor groups, we assume, for example, non-Hispanic white and minority miners (1/3 and 2/3 of the study population respectively) have 85% and 80% acceptance respectively. We used simulation to assess power for Poisson regression analyses where the rate denominator (offset) is the number of miner workdays, assumed to be 95% of possible days. For these conditions, power is 94% for a 5% lower acceptance rate for minority miners. We also used simulation to assess the planned longitudinal analysis of miner acceptance by assuming that miners attended work 95% of the shifts, that initial acceptance is 85% and that there is a linear decline in acceptance over the study to a final acceptance rate of 80%. For repeated measures on about 200 miners, the power to detect a linear decrease to 80% is 95%.

13.2. Specific Aim 2:

Statistical analysis: We will compare screening test performance measures between our real-world study setting and controlled settings (as published by others). We will use a one-sample Exact test for a binomial proportion to test whether sensitivity for the screening test is the same as that published. We will correlate screening test results with quantitative viral loads, and perform Bland-Altman plots to reveal systematic differences between viral loads collected by the two sampling methods.

Power Calculations: If we conservatively estimate identifying 25 true positive miners, using a one-sample Exact test for a Binomial proportion equal to the comparison test, we have the power (>90%) to detect a difference between the screening and the comparison test if the screening test sensitivity is 90% or lower.

13.3. Specific Aim 3:

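### Aim 2 claims over 90% power at 90% sensitivity, but against the published 95% the planned exact test has only about 10–24%

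*Combined protocol and SAP*

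**What the plan says.** Section 13.2 (Statistical analysis) defines the test for Hypothesis 2a: "We will use a one-sample Exact test for a binomial proportion to test whether sensitivity for the screening test is the same as that published". The power paragraph that follows sets the sample size, "If we conservatively estimate identifying 25 true positive miners", describes the null as a proportion "using a one-sample Exact test for a Binomial proportion equal to the comparison test", and concludes that "we have the power (>90%) to detect a difference between the screening and the comparison test if the screening test sensitivity is 90% or lower". It gives no number for the null, no alpha and no sidedness.

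The only published sensitivity in the document is in Section 3.2, which reports interim results against laboratory RT-PCR: the "screening test in controlled settings (in urgent care clinic, hospitalized and nursing home patients) is" at least 95% sensitive. Hypothesis 2a, in Sections 1 and 3.2, is that real-world sensitivity is comparable to that controlled-setting value. The assay itself had not been chosen. Section 2 lists the properties it must have, including "Sensitivity and specificity: At least 80"%.

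**The concern.** A fall from 95% to 90% is a small difference to detect with 25 observations: the expected numbers detected are 23.75 and 22.5. Power above 90% for that contrast is implausible on its face.

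The error runs in the direction that helps the hypothesis. Hypothesis 2a asserts comparability, and the only test named for it is one of equality. The document states no rule for how a non-significant result will be read, but the natural reading is that the test performed as published. A reader who believes the test would have caught a drop to 90% more than nine times in ten will take non-rejection as strong evidence. In fact, a drop to 90%, which doubles the share of infections missed from 5% to 10%, would go undetected 76–90% of the time. Section 3.2 itself names several features of workplace self-collection as potential sources of error, so lost sensitivity is the outcome the aim needs to be able to see.

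**Working it through.** **Inputs**
- n = 25 true positives (Section 13.2).
- Alternative p1 = 0.90; stated power above 90% (Section 13.2).
- Null p0 = published sensitivity (Section 13.2), at least 95% (Section 3.2). I take 0.95 and then test higher values.
- Alpha is not stated for Aim 2. I assume 0.05 and show both one-sided and two-sided (equal-tailed) versions.

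**Method.** Let X be the number detected out of 25. Find the largest c with P(X ≤ c | p0) ≤ 0.05 (one-sided) or ≤ 0.025 (two-sided). Power is then P(X ≤ c | 0.90).

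**Reproducing the plan's figure.** If p0 = 1, any miss rejects, so c = 24 and power = 1 − 0.9^25 = 0.928. This matches the stated figure. To reject at 24 of 25 with a smaller null requires 1 − p0^25 ≤ alpha, that is:
- one-sided: p0 ≥ 0.95^(1/25) = 0.998
- two-sided: p0 ≥ 0.975^(1/25) = 0.999

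The next cut-off down, c = 23, gives power of only 72.9%. Power above 90% at a true 90% therefore needs a null of at least 99.8%.

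**The planned test, p0 = 0.95**

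| Rejects at | P under 95% | Power at 90% | Applies to |
|---|---|---|---|
| X ≤ 20 | 0.0072 | 9.8% | two-sided, equal tails |
| X ≤ 21 | 0.0341 | 23.6% | one-sided 5%; two-sided ordered by likelihood |
| X ≤ 22 | 0.1271 | – | not a 5% test |

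**Higher nulls, since the published value is given as at least 95%**

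| Null | Two-sided power at 90% | One-sided power at 90% |
|---|---|---|
| 95% | 9.8% | 23.6% |
| 97% | 23.6% | 46.3% |
| 99% | 46.3% | 72.9% |

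**What 25 true positives can detect against 95%.** Setting P(X ≤ c | p1) = 0.90 gives p1 = 0.752 for c = 21 (one-sided) and p1 = 0.705 for c = 20 (two-sided).

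**What detecting 90% against 95% would need.** The first n at which exact power reaches 90% is 233 (one-sided) or 279 (two-sided). Exact power is saw-toothed, and the two-sided figure dips below 90% again at n = 280–289, so these are approximate sizes. They are true positives, not miners tested, and the whole intervention cohort is fewer than 250 miners.

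**An example.** Observing 22 of 25 (88%; exact 95% interval 69–97%) gives p = 0.13 against 95% and does not reject.

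**A lower published value.** If the chosen assay's published sensitivity were 90%, a true 90% would be the null itself and rejection could not exceed alpha. At a published 80%, a two-sided test rejects upward only at 25 of 25, because P(X ≥ 24 | 0.80) = 0.027 exceeds 0.025. Power at a true 90% is then about 0.9^25 = 7%.

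**The case against.** The strongest reply is that the sum is right for the null its own sentence names. The power paragraph speaks of the comparison test, not the published value, and Section 3.2 establishes sensitivity by comparison with RT-PCR. If RT-PCR is taken as 100% sensitive, the null is 100% and 92.8% follows. That probably explains the figure, and it makes the fault a mismatch of nulls rather than a slip of calculation.

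It does not rescue the claim. The analysis sentence just above says the purpose is "to test whether sensitivity for the screening test is the same as that published", and Hypothesis 2a says the same. A test against 100% would also reject an assay performing exactly at 95% in 1 − 0.95^25 = 72% of studies, so it cannot assess comparability.

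Other points stand in part:
- 95% is the low end of an interim figure, and the assay was not final, so 10–24% is specific to that null. The higher nulls above show the conclusion holds up to 99%.
- Alpha and sidedness are missing, so any recomputation must assume them. No exact version at 0.05 exceeds 24% against 95%.
- No passage says that non-rejection will be reported as comparability. That is an inference from the form of the hypothesis.
- Aim 2 does not carry the outcome labelled primary, which is incident seropositivity in Aim 3, and the number of positives depends on infections occurring. Correcting the figure would not change enrolment. This limits the reach of the error but leaves the stated power wrong.

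**Conclusion.** The concern holds. The stated power belongs to a test against about 100%, not to the test against the published value that Section 13.2 plans. With 25 true positives, a 95% null and alpha 0.05, power at 90% sensitivity is 9.8% (two-sided) to 23.6% (one-sided), so the stated 90% is roughly four to nine times too high. For nulls between 95% and 99% the range is 9.8% to 72.9%, and the stated figure is never reached. The assumptions are the 5% alpha, the 95% reference from Section 3.2, and the plan's own count of 25. The low power is not in itself the error. The errors are that it is stated as high, and that a non-significant test of equality is left to support a claim of comparability.

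**What to change.** 1. In Section 13.2, state the null value, alpha and sidedness, and replace the power sentence. For example: with 25 true positives and a reference sensitivity of 95%, the exact test at 5% has about 10% power (two-sided) or 24% power (one-sided) if true sensitivity is 90%, and reaches 90% power only if true sensitivity is about 71% (two-sided) or 75% (one-sided) or lower.
2. Use one term for the reference throughout, and take its value from the assay actually selected, recomputing the power if it is not 95%.
3. Base Hypothesis 2a on the exact confidence interval for sensitivity, claiming comparability only if the lower limit exceeds a bound fixed in advance. The investigators must choose and justify that bound. With 25 true positives, even 25 of 25 gives a two-sided 95% lower limit of 0.025^(1/25) = 86.3%, so a bound above that could not be met.

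Items 1 and 2 are wording only. Item 3 is also a change of text with no new data, but it replaces the decision criterion and makes comparability harder to claim. If item 3 is not adopted, items 1 and 2 are still needed, and the report should say that non-rejection with 25 positives does not show comparability.

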Hypothesis 2: The sensitivity of the screening test in a real-world study setting is a) comparable to that described by others in controlled settings, and b) positively associated with viral load in upper respiratory specimens (latter measured in nose and nasopharynx using quantitative reverse transcriptase-polymerase chain reaction or RT-PCR).

Specific Aim 3: To determine the effectiveness and implementation costs of frequent point-of-care molecular workplace surveillance on reducing incident infection rates of SARS-CoV-2.

Hypothesis 3A: Frequent point-of-care molecular testing over up to twelve months in the intervention mine will result in lower incident seropositivity rates compared to the control mine. *Hypothesis 3B:* Frequent point-of-care molecular surveillance in the intervention mine is cost-effective compared to the control mine.

Specific Aim 4: To determine novel predictive factors associated with incident SARS-CoV-2 infection, tests, and vaccination in miners. *Hypothesis 4A:* Miners with incident infection demonstrate less frequent use of cloth face-coverings outside the workplace, greater mine dust exposure intensity, presence of dust-related lung

PROTOCOL TITLE: Keeping rural minority ‘essential’ workplaces open safely during the COVID-19 pandemic: The role of frequent point-of-care molecular workplace surveillance for miners

disease, and racial/ethnic minority status than those not infected. *Hypothesis 4B:* Test and vaccine uptake by miners is predicted by specific barriers and facilitators.

Hypothesis 4B involves a separate but related study, titled “Facilitators and barriers for COVID-19 testing uptake and its impact on vaccine uptake in a rural diverse essential workplace ([name]/[name], Co-PIs; NIH 1U23MD016258-01 RADx-UP Central Data Coordination Center Rapid Research Pilot Project)”. The objective is to determine facilitators and barriers to COVID-19 test uptake, and the impact of the latter on vaccine uptake, at a surface coal mine. This study involves the administration of a questionnaire once between 6 and 12 months time point.

2. Background

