4.2. Exclusion Criteria

- Unable or unwilling to provide and sign Informed Consent Form
- < 18 years of age.

PROTOCOL TITLE: Keeping rural minority ‘essential’ workplaces open safely during the COVID-19 pandemic: The role of frequent point-of-care molecular workplace surveillance for miners

We will not recruit or enroll pregnant women, incarcerated individuals, minors, or adults unable to consent.

5. Number of Subjects

Less than 600 subjects will be recruited at all mine sites in this longitudinal study. Of these, less than 250 miners will be recruited from the Peabody El Segundo mine in McKinley County, NM at the edge of Navajo Nation (i.e., intervention mine). The remaining less than 350 miners will be recruited from the Peabody Caballo and Rawhide mines at Campbell County, WY (i.e., control mine). Both surface coal mines, operated by the same company, have similar engineering, administrative and personal protective measures in place, including SARS-CoV-2 symptom & fever screening. While there will be frequent point-of-care molecular testing at the intervention site, seroprevalence (baseline, 3, 6, and 12 m) will be measured as an outcome at both sites.

6. Study Timelines

The duration of individual subject’s participation in this research is estimated to be approximately 12 months from the time they give and sign informed consent. We anticipate that all study participants will be enrolled in the first month of the recruitment and enrollment. Below are milestones with estimated dates of completion. The dates may be adjusted as necessary depending on the completion of previous milestones.

Milestone 1: Completion of planning, contracts, purchase of tests and supplies, protocols and IRB approval: by January 2021.

Milestone 2: Recruitment and collection of data: January 2021 through March 2022 (anticipated).

Milestone 3: Data analysis and dissemination: July 2021 through November 2022 (anticipated).

7. Study Endpoints:

7.1. Specific Aim 1:

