Expected outcomes: We anticipate that the screening test results can be confirmed by detecting the SARS-CoV-2 load, within the limit of RT-qPCR detection. Based on our preliminary data (Fig. 2), our detection limit is ≥ 100 viral copies per mL (32). This level of detection is contingent on obtaining enough sample material. It remains unclear if a self-collected nasal swab collected in a real-world setting will consistently yield enough sample material to detect SARS-CoV-2. Since we will incorporate a primer and probe for the detection of the human ribonuclease P gene in our assay, we can directly determine if there is sufficient sample material on the screening test for the detection of SARS-CoV-2. The study design will also allow us to determine if the level of the virus on the nasal swab, self-collected in a real-world setting, is comparable in its ability to detect SARS-CoV-2 as that of a health personnel-collected NP swab.

7.3. Specific Aim 3:

Predictor and Outcome variables: The predictor variable is the mine status (intervention vs. control). The primary outcome is any *new* seropositivity for SARS-CoV-2 IgM or IgG at 3, 6, or approximately 12 months relative to baseline. The serologic test (depending upon availability, finalized using NIH recommendation) allows for the qualitative detection of IgG or IgM antibodies (separately) against SARS-CoV-2, indicating recent (IgM: 3-5 days) or prior infection (currently unknown). We will also study the presence of symptoms or fever, irrespective of infection status, as an alternative study outcome for hypothesis 3A. Costs of the test-based surveillance program, employee absenteeism patterns, and mine coal production will contribute towards defining the outcome variables for hypothesis 3B. At a minimum, a valuable outcome is to determine surveillance program costs, which have not been previously established for this rural industry setting, organization size, or proposed surveillance frequency. Additionally, variance in outcome measures—defined as employee days lost due to incident infection, mine productivity, and reduction in worksite infection rate—across the two sites will be used to estimate the cost-effectiveness of the intervention. Database management and timeline are similar to that for Aim 1.

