Predictor and Outcome variables: The predictor variable is the mine status. The primary outcome is any new seropositivity for SARS-CoV-2 IgM or IgG at 3, 6, or 12 months relative to baseline. The test allows for the qualitative detection of IgG and/or IgM antibodies (separately) against SARS-CoV-2, indicating recent (IgM: 3-5 days) or prior infection (currently unknown). The tests have positive percent agreements of 97% and 87% and negative percent agreements of 98% and 99% for IgG and IgM, respectively, compared to oropharyngeal swab RT-PCR. We will also study the presence of symptoms or fever, irrespective of infection status, as an alternative study outcome for hypothesis 3A. Costs of the test-based surveillance program, employee absenteeism patterns, and mine coal production will contribute towards defining the outcome variables for hypothesis 3B. At a minimum, a valuable outcome is to determine surveillance program costs, which have not been previously established for this rural industry setting, organization size, or proposed surveillance frequency. Additionally, variance in outcome measures—defined as employee days lost due to incident infection, mine productivity, and reduction in worksite infection rate—across the two sites will be used to estimate the cost-effectiveness of the intervention. Database management and timeline are similar to that for Aim 1.

PROTOCOL TITLE: Keeping rural minority ‘essential’ workplaces open safely during the COVID-19 pandemic: The role of frequent point-of-care molecular workplace surveillance for miners

Covariates: Baseline seropositivity, vaccination status, other host susceptibility and vulnerability factors outlined in Table 1, and daily community prevalence and incidence, will be studied as covariates in multivariable models (35).

Statistical analysis: Chi-square tests will examine whether relative frequencies of incident seropositive miners are the same at 3-months, 6-months, and 12-months for the two mine types, using $\alpha=0.025$ to account for the two tests. Generalized linear models for repeated binary outcomes will be used to assess how covariates are associated with seropositive status over time.

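### The Aim 3 primary outcome counts any new antibody positivity as infection and has no rule for vaccination; if the assay detects vaccine antibody, the unadjusted between-mine chi-square mixes vaccine uptake with infection

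*Combined protocol and SAP*

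**What the plan says.** Aim 3 (Section 1) concerns incident SARS-CoV-2 infection. Its outcome in Section 13.3, and in nearly the same words in Section 7.3, is serological: "The primary outcome is any new seropositivity for SARS-CoV-2 IgM or IgG at 3, 6, or 12 months relative to baseline". A positive result is interpreted as "indicating recent (IgM: 3-5 days) or prior infection (currently unknown"); vaccination is not mentioned as a source of antibody.

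Section 7.3 leaves the assay open: "The serologic test (depending upon availability, finalized using NIH recommendation) allows for the qualitative detection of IgG or IgM antibodies". No section names the antibody target. The agreement figures in Section 13.3 (97% and 87% positive, 98% and 99% negative, for IgG and IgM) are "compared to oropharyngeal swab RT-PCR", so they say nothing about response to vaccination.

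The first between-mine analysis in Section 13.3 is unadjusted: "Chi-square tests will examine whether relative frequencies of incident seropositive miners are the same". Vaccination enters elsewhere, as a covariate for multivariable models: "Baseline seropositivity, vaccination status, other host susceptibility and vulnerability factors outlined in Table 1". Section 13.4 plans repeated-binary models for incident seropositivity with the Aim 3 covariates and with mine type.

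Vaccination during follow-up is expected. Section 6 gives "Recruitment and collection of data: January 2021 through March 2022 (anticipated"). The phone app asks about vaccination each shift at both mines (Sections 12 and 12.3), and Section 13.1 models it as time-varying.

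**The concern.** An antibody test measures infection only if infection is the only thing that can turn it positive. Once vaccination starts, that depends on which antibody the assay detects, and the plan does not say. With an assay that responds to vaccine antibody, a miner who is vaccinated and never infected becomes a primary-outcome event.

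Two things follow for the chi-square. Equal uptake at both mines adds the same non-infection events to each arm and buries the contrast. Unequal uptake creates a contrast of its own, in either direction. Hypothesis 4A is affected too, because Section 7.4 takes its outcome from Aim 3.

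**Working it through.** **Inputs from the documents.** At most 250 intervention and 350 control miners (Section 5; the text says fewer than these, so they are upper limits). Incident seropositivity 5% vs 9%, alpha 0.025, claimed power 80% (Section 13.3). Baseline seropositivity 10% and 5% (Section 13.3).

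**Assumptions, since the documents give no values.** Uptake v after baseline at each mine; share s of vaccinees who turn positive; vaccination independent of infection.

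**Step 1: the plan's own figure.** Two-proportion chi-square, pooled null standard error, two-sided 0.025 (z = 2.2414).
- Pooled rate = (250×0.05 + 350×0.09)/600 = 0.0733. SE0 = 0.02159, SE1 = 0.02059.
- Power = Φ[(0.04 − 2.2414×0.02159)/0.02059] = Φ(−0.41) = 34%.

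The claimed 80% does not reproduce; it needs about 12.25% in the control mine. That is a separate matter. Both bases are carried below so that the low 34% does not drive the result.

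**Step 2: effect of counting vaccine antibody.** Observed rate = 1 − (1 − p)(1 − s·v), with s = 1.

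| Equal uptake | Observed rates (from 5% vs 9%) | Chance of benefit, 5% vs 9% | Chance of benefit, 5% vs 12.25% |
|---|---|---|---|
| 0% | 5.0% vs 9.0% | 34% | 80% |
| 10% | 14.5% vs 18.1% | 14% | 42% |
| 20% | 24.0% vs 27.2% | 9% | 25% |
| 30% | 33.5% vs 36.3% | 6% | 16% |
| 50% | 52.5% vs 54.5% | 4% | 9% |

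Unequal uptake (intervention vs control):
- No true effect, 5% at both mines, uptake 30% vs 40%: observed 33.5% vs 43.0%. Φ[(0.095 − 2.2414×0.04040)/0.03989] = 54% false benefit, against a nominal 1.25%. At 30% vs 35% it is 15%.
- True 5% vs 9%, uptake 40% vs 30%: observed 43.0% vs 36.3%. Significant harm 28%, benefit about 0%.

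Partial detection (s = 0 / 0.25 / 0.50 / 1):
- Benefit at 5% vs 9% and equal 30% uptake: 34 / 16 / 11 / 6%.
- False benefit at 30% vs 40%: 1.25 / 8 / 19 / 54%.

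At s = 0 there is no distortion.

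**Step 3: what the planned adjustment would do.** A vaccination-stratified Mantel-Haenszel test stands in for the covariate models of Sections 13.3 and 13.4, with vaccination recorded accurately (simulation, same sample sizes and alpha).
- No true effect, uptake 30% vs 40%: false benefit 1.1% (chi-square 54%).
- 5% vs 9%, uptake 40% vs 30%: significant harm about 0.01% (chi-square 28%); benefit 20% (chi-square about 0%).
- 5% vs 9%, equal 30% uptake: benefit 23% (chi-square 6%). If half of vaccinees turn positive, 14% (chi-square 11%).

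The 23% has a simple source. When every vaccinee is positive, the vaccinated stratum carries no information, leaving 250×0.7 = 175 vs 350×0.7 = 245 miners, for which the Step 1 formula gives 23%.

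**Step 4: cost of counting events only up to vaccination.** Baseline-seronegative miners: 250×0.90 = 225 and 350×0.95 = 332.5. Expected events: 225×0.05 + 332.5×0.09 = 41.2. With 30% or 50% of miners censored, 28.8 or 20.6 events remain, and power goes from 31% to 21% or 15%. These use the at-risk numbers, so they are not like for like with Step 3.

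**The case against.** The strongest reply is that the plan already handles vaccination. It is recorded at both mines, it is a listed covariate, and Section 13.4 puts it in a model with mine type for this same outcome. Step 3 shows that this largely stands: with accurate recording, such a model removes nearly all of the false benefit and false harm. Three things remain. Those models are not the lead between-mine test. They do not restore full power. And they cannot tell whether a vaccinated, antibody-positive miner was infected; censoring at vaccination cannot either.

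A reader might go further than the documents allow in four ways.
- That the whole plan could hide, reverse or invent an effect. This describes the unadjusted chi-square only, for the reason just given.
- That the plan itself anticipates different uptake between mines. The companion study in Section 1 examines "facilitators and barriers to COVID-19 test uptake, and the impact of the latter on vaccine uptake", but at one surface coal mine, and Section 8 limits its questionnaire to New Mexico. No section compares uptake between mines; a difference is an assumption here.
- That the app misses off-shift vaccinations because Section 12.3 refers to a 24-hour history. The Section 12 table refers to vaccination history, and Sections 7.1 and 13.1 take prior vaccination from the app, which favours a cumulative record. The wording needs reconciling, but it does not support an estimate of missed vaccinations.
- That the bias is established. It depends on an assay property that the documents do not give.

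The illustration also places all vaccination after the baseline draw. A miner already antibody-positive from earlier vaccination could not become a new event.

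**Conclusion.** The point holds in conditional form and should be fixed. With high confidence: the primary outcome treats any new IgM or IgG positivity as infection, names no antibody target, has no rule for positivity after vaccination, and is first compared between mines without adjustment. Whether this biases the result depends on the assay: if vaccine antibody is not detected, there is no distortion.

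If it is fully detected, the chi-square is unreliable at modest uptake even when the mines are balanced (benefit 34% down to 14 / 9 / 6 / 4% at 10 / 20 / 30 / 50%). A 10-point gap with no true effect gives 54% false benefit in the 30% vs 40% example. These sizes rest on assumed uptake, detection share and timing, independence of vaccination and infection, and the maximum sample sizes. They show how sensitive the test is and do not predict the trial's result.

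**What to change.** 1. In Sections 7.3 and 13.3, define the primary outcome as infection-induced seroconversion among miners seronegative at baseline. State the antibody target, and use a read-out that does not respond to vaccine antibody where one is available. The chi-square can then stay.
2. If the assay used does detect vaccine antibody, do not let the unadjusted chi-square carry the Aim 3 conclusion. Make the lead comparison either one that counts seroconversion only up to first reported vaccination, or the vaccination-adjusted mine comparison already planned. Use the app data, which are collected at both mines. State that power is lower and that vaccination may be informative.
3. Reconcile the 24-hour wording in Section 12.3 with the vaccination-history wording in Sections 7.1, 12 and 13.1, so that the date of first vaccination is captured.

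The wording and the choice of lead analysis cost little. The assay requirement is cheap only if no draws have been tested. Section 7.3 still treats the choice as open, but Sections 23 and 25 (a payment absent from the consent, and reconsent at or after six months) suggest revision after enrolment began. The real price of step 2 is power: in the illustration, 31% falls to 21% or 15% with 30% or 50% censored. Retesting banked blood is optional and not part of the cheap fix, since Section 17 makes banking subject to consent and a fingerstick may leave nothing to bank.
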